4.2 Application of Investigational Products and Control Products

The investigational products have been granted with 510K clearance by the country of origin USA in 2015. Currently the products have been marketed in many countries, however, due to the short marketing time, they have not been reported in literature yet.

Both the control products ██████████ and ██████████ are non-barbed, triclosan-coated sutures. Such sutures have been marketed in China since 2014. As mentioned above, the efficacy and safety of such sutures have been sufficiently validated ^[11-12, 16].

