5.3 Study Population

This clinical study will include subjects who undergo thyroid surgery via an anterior cervical arch incision (Kocher's incision).

6. Indications and Contraindications, Precautions

6.1 ██████████:

[Indication]: It is indicated for use in soft tissue approximation where the use of absorbable sutures is appropriate.

[Contraindications]: It is not to be used where prolonged (beyond six weeks) approximation of tissues under stress is required and is not to be used for fixation of or in conjunction with prosthetic

devices (e.g. heart valves or synthetic grafts) that are nonabsorbable in nature. This device, being absorbable, should not be used where extended approximation of tissue under stress is required, such as in fascia. The device should not be used in patients with known allergic reactions to IRGACARE®* MP (triclosan).

[Precautions]: The device contains a fixation loop and barbs to anchor tissues and do not require knots to secure the device. Tying of knots on the barbed section of the device will damage the barbs and potentially reduce their efficacy. For the device to function properly, the device must first be anchored in robust tissue using the fixation loop. Then subsequently engage the barbs into the tissue in a standard closure pattern. When completing placement of the barbed segment in subcuticular tissue, take at least one additional pass in the reverse direction to lock the device in place. In all other tissue layers, take at least two passes in the reverse reaction to lock the device in place.

Avoid contacting the device with other materials (e.g. surgical gauze, drapes, etc.) in the surgical field to prevent ensnaring on the barbs. If the barbs catch, carefully pull the material in the opposite direction of the needle to disengage it from barbs.

When using the device subcutaneously, the device should be placed as deeply as possible in order to minimize erythema and induration normally associated with absorption.

Care should be taken to avoid damage when handling the device. Avoid crushing or crimping the suture material with surgical instruments (e.g. needle holders or forceps). Do not attempt to remove memory in the polymer by running fingers down the suture material as this can damage the barbs.

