7.1.5 Subject Selection

1) Inclusion criteria

1. The subject is ≥ 18 , and < 70 years old
2. Planned open thyroid surgery, adopting an anterior cervical curved incision (Kocher's incision);
3. Subject who volunteers to participate in this study, follows the study requirements and follow-up visit and signs the written Informed Consent Form voluntarily;
4. Subject who agrees to not schedule any elective surgical operation except the study surgery before the study is completed;
5. The investigator considers the subject's expected postoperative survival time is not less than 3 months.

2) Exclusion Criteria

1. Female subjects who are pregnant or lactation at screening;
2. Preoperative clinical staging shows stage IV thyroid cancer, or cervical lymph nodes dissection is planned;
3. Suspected or confirmed anaplastic thyroid cancer;
4. Peripheral vascular disease affecting blood supply of the neck;
5. Active infectious collagenosis (e.g. scleroderma), or any other disease that would interfere with the wound closure;
6. Fasting plasma glucose (FPG) ≥ 7.7 mmol/L;
7. History of coagulation diseases;
8. Current oral or intravenous antibiotic therapy for existing disease or infection;
9. History of immunosuppressant use (e.g. steroids) within the last 6 months;
10. Chemotherapy or radiotherapy within the last 6 months, or planned chemotherapy or radiotherapy during the study;
11. Personal or family history of keloid formation or hyperplasia;
12. Current participation in any other drug (within 30 days or within 5 half-lives of the investigational drug) or device clinical study;
13. History of any thyroid surgery, except thyroid fine-needle aspiration biopsy;
14. Planned use of skin adhesive at the incision site;
15. The subject is not suitable for participating in this study for any other reasons, as judged by the investigator.

3) Criteria and procedure of Study Discontinuation

The criteria for Subject's Discontinuation from Study include, but are not limited to:

1. Withdrawal of consent: Subject decides to withdraw from the study. This decision must be "self-determination" and should be documented;
2. Investigator's judgement: The Investigator may determine the withdrawal of subjects from the study according to reasonable medical judgement and such withdrawal may benefit the subject mostly.

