7.2 Trial Flow Chart

7.2.1 Flow diagram of clinical trial

The schedule and events table of the trial is as follows:

Project	V1	V2	V3	V4	V5	Withdraw visit
Event/time point	Screening /baseline: within 14 days prior to surgery	Randomization: prior to surgery	Surgery	5-7 days after surgery	28-35 days after surgery	For subjects randomized but without any of study sutures used and for subjects who withdraw ICF ¹

Informed consent	X					
Demographic information	X					
Randomization		X				
Inclusion & Exclusion Criteria	X	X				
Fasting plasma glucose test ^a	X					
Blood/urine pregnancy test ^b	X					
Medical Record/ Surgical history ^c	X	X				
Physical examination	X					
Concomitant Medications ^d	X	X	X	X	X	
Surgical data ^e			X			
Concomitant treatment			X	X	X	
Imaging data of incision ^f				X	X	
Discharge date				X		
Wound healing grade assessment ^g				X		
Modified Hollander Wound Evaluation Scale ^g					X	
Postoperative incision pain score				X	X	
EQ-5D-5L	X			X	X	
SSI/ASEPSIS score				X	X	
Complications of incision ^h				X	X	
Adverse event		X	X	X	X	X
Product complaint			X	X	X	X
End of study					X	X

- a. The result of the examination should be completed within 7 days prior to the signing of ICF.
- b. Applicable to female subjects of childbearing age (less than 2 years post-menopausal). The result of the examination completed within 7 days prior to the signing of ICF is acceptable.
- c. Disease newly diagnosed or existing within the period from 30 days prior to the signing of ICF to randomization are collected.
- d. Concomitant medications used within the period from 7 days prior to the signing of ICF to the end of the study will be documented, excluding medications for surgical anesthesia.
- e. The surgical data should include suturing time, length of operation, total operating room time, intraoperative suture performance indicators (collected data of the second case using ██████████ and ██████████ from each Investigator), and intraoperative use of suture devices.
- f. At V4, a picture of complete neck anterior view containing full length of the incision should be collected; at V5, 5 pictures of incision should be collected [including a picture of complete neck anterior view containing full length of the incision, a picture taken parallel to the incision plane, a picture taken at a 45° angle to the incision plane, and incision lateral view pictures of both sides (one for each)] for assessment done by independent Central Imaging evaluators.

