7.2.3 Study Procedures

1) Visit 1 – Screening/ Baseline visit

The following screening procedures should be completed prior to any study procedure:

- The subject must be given enough time to review and sign the ICF;

- Collection of demographic information (e.g. date of birth, gender, ethnic origin, etc.);
- Review and collection of medical/surgical history;
- Urine/blood pregnancy test: The result of the examination completed within 7 days prior to the signing of ICF is acceptable. If multiple examinations are completed, the result of the examination closest to the time of operation shall prevail;
- Fasting plasma glucose test: The result of the examination completed within 7 days prior to the signing of ICF is acceptable. If multiple examinations are completed, the result of the examination closest to the time of operation shall prevail;
- Review/collection of inclusion/exclusion criteria, and determining whether the subject meets the criteria or not;
- Physical examination: Including body height, body weight, physical examination results of the head and neck, and other contents;
- Concomitant medications: Medications started within 7 days prior to the signing of ICF or currently used
- EQ-5D-5L。

a. Screening

Subjects will be consented prior to any study-specific screening procedures being conducted. Subjects will be considered enrolled into the study upon satisfaction of the following criteria:

- Completion of the informed consent process;
- It is determined by the investigator that the subject meets all inclusion criteria and does not meet any exclusion criteria (Section 7.1.5). The verification must be conducted by the Principal Investigator (PI) and/or authorized investigators prior to randomization.

b. Screen Failures

Subjects who signed the ICF and were screened but not successfully randomized will be considered screen failures. For subjects who are determined to be screen failures, only the following data will be collected:

- Informed consent date;
- Demographic information (age, race, gender, and ethnicity);
- Reason for screening failure.

2) Visit 2 -Randomization

The following information must be obtained during randomization:

- Confirmation of inclusion / exclusion criteria;
- Update of medical/surgical history (prior to randomization);
- Randomization: Central randomization prior to the surgical procedure;
- Concomitant medications;
- Adverse event (AE) (collected since randomization).

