Randomization will occur if the patient meets all inclusion criteria and does not meet any exclusion criteria.

The central randomization system will be used in this study, so that subjects will not know their treatment group allocation. Each subject will be randomized to one of the three treatment groups according to the allocation ratio of 1:1:1, and the only difference between the investigational groups and control group lies in the suture material. Each group will include approximately 167 subjects.

3) Visit 3-Surgery

The following information must be obtained during the surgical procedure:

- Surgical data, including:

- Use: Including the code and quantity of study product used, and tissue layer at which the study product is used;
- Suturing time: It is defined as the time required from the first needle insertion for stitching ribbon muscles to the completion of intradermal suture (min);
- Length of operation: It is defined as the time from the incision of skin to the closure of skin (min);
- Total operating room time: It is defined as the time from the start of anesthesia on the subject to the time of leaving the operating room (min);
- Intraoperative suture performance indicators (using VAS scale, see Annex 4-2, collected data of the second case using ██████████ and ██████████ from each Investigator): Ease to pass through tissues, surgical operation profile (including surgical handfeel), suture memory, and wear resistance of suture;
- Concomitant medications: Excluded intraoperative medications for anesthesia;
- Concomitant treatment;
- AEs;
- Product complaints.

Surgical procedures

a. Open thyroid surgical procedure via the anterior cervical curved incision (Kocher's incision):

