8.8 Selection Criteria and Reason of Subjects Included in the Analysis

All subjects that meet the inclusion/exclusion criteria are considered to meet the requirements for recruitment.

Three analysis sets in the study are defined for this study, as follows:

- FAS consists of all the enrolled subjects who were randomized and for whom the randomized suture materials were used for incision closure.
- PP (evaluable) Set contains all the subjects in the FAS who have no major protocol

deviation, have data available for primary efficacy endpoint and do not meet any of the following criteria:

- Subject undergoes any of the following procedures, in addition to thyroidectomy:
 - 1、 Any surgical procedure which require additional neck incisions or extend the original incision;
 - 2、 Cervical lymph node dissection (except the dissection of lymph nodes in the VI area);
 - 3、 Other unplanned surgical procedures (except the procedure that the investigator doesn't think it will affect the original incision's healing)
- Subject's intraoperative frozen pathology or postoperative paraffin section pathology suggests anaplastic thyroid cancer;
- Subject receives any surgical procedures that lead to re-opening of the cervical incision during the period from the wound closure to the completion of study, except for surgeries related to surgical incision complication or study device.
- Safety Set contains all the enrolled subjects who receive surgery.

Major protocol deviations are deviations that have an impact on the primary endpoint assessment or randomization. These will be determined prior to database lock.

The analysis of primary efficacy endpoint will be performed using FAS and PP Sets. However, while the primary analysis is based on the PP Set, FAS analysis will only be used as supplemental analysis.

The secondary efficacy endpoints will be analyzed using the FAS, while the safety endpoints will be analyzed using the Safety Set.

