12.1 Ethical Concerns

CONFIDENTIAL

Ethical issues involved in this study have been stipulated according to China's laws and regulations and international consensus such as the Declaration of Helsinki, the protocol design has taken ethical principles into full consideration, and the rights, safety and health of trial subjects are the most important concerns. The specific contents should at least include:

- 1) Regulations to make sure subjects are fully informed
- 2) Regulations that respect and protect subjects' privacy, and that keep records possibly identifying subjects confidential
- 3) The production of investigational product should meet the relevant requirements of applicable quality management system for medical devices; the processing and storage of investigational product should meet the requirements of IFU and SOP. The investigational product should be used according to the approved protocol and related operation instructions. The reference product should be used to ensure the safety of subjects to the maximum extent.
- 4) Qualified clinical study sites and investigators should be selected, and investigators should make medical decisions that are in the best interest of subjects
- 5) In the inclusion/exclusion criteria of the study, inclusion criteria for subjects of different groups should be identical; subjects who withdraw from the study will not affect the treatment of disease; Subjects who suffer from study-related injury will be given appropriate treatment and compensation (see ICF)
- 6) Before any subject is recruited, the study protocol and its amendments, ICF and other study-related documents applicable must be submitted to the corresponding EC for review and must obtain written comments from the EC.

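### Known triclosan allergy rules out both investigational sutures, yet no exclusion criterion names it and no screening item asks about it

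*Protocol*

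**What the plan says.** Protocol sections 6.1 and 6.2 each list, under contraindications, the same sentence for the two investigational devices: "The device should not be used in patients with known allergic reactions to IRGACARE®* MP (triclosan". Section 4.2 says that both control products "are non-barbed, triclosan-coated sutures". The documents print no triclosan contraindication for the control products.

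The synopsis and section 7.1.5 each list 15 exclusion criteria. Numbers 1 to 14 are specific, and none mentions triclosan, allergy or hypersensitivity. Number 15 is the general one: "The subject is not suitable for participating in this study for any other reasons, as judged by the investigator".

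Section 7.2.3 makes these criteria the condition for entry: "Randomization will occur if the patient meets all inclusion criteria and does not meet any exclusion criteria". Section 8.8 adds: "All subjects that meet the inclusion/exclusion criteria are considered to meet the requirements for recruitment".

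At Visit 1 the relevant item is "Review and collection of medical/surgical history". Footnote c to the schedule in section 7.2.1 defines what that history covers: "Disease newly diagnosed or existing within the period from 30 days prior to the signing of ICF to randomization are collected".

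**The concern.** Most of the section 6 contraindications describe the surgical setting: tissue under prolonged stress, fascia, or use with non-absorbable prostheses. Triclosan allergy is the only one that is a characteristic of the patient. It can be established before randomisation, so the eligibility criteria are its natural place.

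What is at stake is subject safety. If nobody asks, a patient who under section 6 should receive neither investigational suture could be enrolled, randomised and possibly exposed. The control arm offers no escape, since its sutures also carry triclosan.

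**Working it through.** The point involves no formula, and the plan gives no figure to reproduce. The check sets the contraindication against each place in the protocol where it could affect entry.

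| Place in the protocol | Items | Items naming triclosan or allergy |
|---|---|---|
| Sections 6.1 and 6.2, contraindications | 2 investigational devices | 2 |
| Synopsis, exclusion criteria | 14 specific + 1 catch-all = 15 | 0 |
| Section 7.1.5, exclusion criteria | 14 specific + 1 catch-all = 15 | 0 |
| Section 7.2.3, Visit 1 list | 9 | 0 |
| Section 7.2.3, Visit 2 list | 5 | 0 |

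The nine Visit 1 items are consent, demographics, history, pregnancy test, glucose test, criteria review, physical examination, concomitant medications and EQ-5D-5L. The five Visit 2 items are criteria confirmation, history update, randomisation, concomitant medications and adverse events.

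1. *Could another specific exclusion cover it?* The nearest is number 5, which concerns collagenosis and other disease that would impair wound healing (synopsis) or closure (7.1.5). It does not name allergy. It does correspond to a softer device warning in section 7.2.2, that use may be inappropriate where healing may be delayed. So a cautionary warning has a matching criterion while an outright contraindication has none.

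2. *Does the device-use section supply a reminder?* Section 7.2.2 sets out indications, operation, warnings and precautions for both devices but does not repeat the triclosan contraindication. An investigator working from the eligibility list, the visit procedures and section 7.2.2 would not meet it.

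3. *Would the history item bring it out?* Footnote c could take in a standing allergy as something existing in the window, but it does not ask for one.

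4. *Does allocation matter?* No. By section 4.2 the control sutures are triclosan-coated, so the question has to be settled before randomisation.

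5. *What happens if the allergy is recognised after randomisation?* The protocol has a route: withdrawal on the investigator's judgement (section 7.1.5) and the withdraw visit (section 7.2.3). But section 7.1.5 does not allow replacement of withdrawn subjects. A subject whose wound is not closed with the randomised suture also falls outside the full analysis set defined in protocol section 8.8. Asking before randomisation avoids both.

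**The case against.** The strongest reply is that exclusion 15 is itself an entry criterion. Section 6 gives an investigator who knows of the allergy a clear ground to call the patient unsuitable. Section 7.2.3 requires authorised investigators to verify eligibility before randomisation, and Visit 2 confirms it again. Read together, these provisions do stop a case the investigator already knows about. For the same reason the entry sentences in sections 7.2.3 and 8.8 do not show that an allergic patient would pass, because the criteria they refer to include number 15.

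The Visit 1 count is also weak as separate evidence. The list is written by category and does not name keloid history, coagulation disease or prior thyroid surgery either, although all three are exclusions. The difference is that those reach the investigator through the criteria review, because the criteria name them. Triclosan allergy does not, so the Visit 1 gap follows from the missing criterion and is not a second defect.

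Other text restrains use of the device. Section 12.1 says "The investigational product should be used according to the approved protocol and related operation instructions", section 21.2 obliges the investigator to follow the protocol and protect subjects, and section 11 provides for sponsor training. These bear on use and conduct. None is an entry criterion, and none helps if the allergy has not come to light.

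Finally, the instructions for use, e-CRF and consent form could contain a prompt. That cannot be checked here. Even if one does, the protocol's own criteria should agree with its own contraindication.

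What stands of the objection is that a known case can be stopped under the present text. What does not stand is that the text makes it likely the case becomes known.

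**Conclusion.** The concern holds, at minor severity. The protocol contraindicates both investigational sutures in known triclosan allergy, and the only eligibility criterion that can act on this is a discretionary one with no prompt behind it. The consequence is avoidable enrolment of a contraindicated patient, and possible exposure if nobody asks.

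The size in patients is not estimated, because the documents give no prevalence of triclosan allergy. No effect on bias, type I error, power or sample size is expected. The conclusion on the wording is firm. The conclusion on possible exposure assumes that no prompt exists in the instructions for use, e-CRF or consent form.

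**What to change.** Add *known allergic reaction to triclosan (IRGACARE MP)* as a named exclusion criterion in the synopsis and in section 7.1.5, and add a question about prior triclosan reactions to the Visit 1 procedures in section 7.2.3.

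The cost is one criterion in two places and one screening question. The expected loss of recruitment is negligible, and the sample size and analysis do not change.

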7.1 Trial Design

7.1.1. Trial Objective

The primary objective of the study is to evaluate the of ██████████ or ██████████
██████████ in thyroid surgery to suture surgical incision.

7.1.2 Trial Method Selection and Its Rationale

According to the regulatory requirements of the Guidelines for Technical Review of Absorbable Surgical Suture Registration, a prospective, randomized controlled design should be adopted to compare the investigational device with launched product. Therefore, this study adopts a prospective, multicenter, randomized controlled trial design.

7.1.3 Measures to Reduce and Avoid Bias

In the study, central randomization will be adopted to randomly assign eligible subjects to one of the three groups: investigational group 1, investigational group 2 or control group according to the same inclusion/exclusion criteria to reduce the impact caused by unknown confounding factors and avoid selection bias.

Study blinding is as follows:

- Subject: Subjects are informed prior to surgery that they will be randomized to any of the study groups with equal probability, and during the surgery, a blinding method will be adopted for them.
- Investigator responsible for incision suture: Considering the investigational groups and

[PROTOCOL VERISON AND DATE] V2.0/2019-09-30

control group use different shapes and usages of suture, it is impossible to blind investigators who are responsible for suturing.

- Central evaluator: Imaging data will be submitted to Imaging Center for assessment to assess the primary endpoint and the modified Hollander score among secondary endpoints. The Central Imaging evaluators will be blinded.
- Monitor: As the product information is specified on the detachable label supplied with the product and instrument counting and source document verification is - done with the study product inventory records and subject's medical record, the monitor will not be blinded.

In addition, this study will collect data about objective measures, study related information will be recorded in the source medical records as detailed as possible, the monitor will pay attention to verifying the data in the source medical records during the monitoring process, investigator training will be strengthened, and investigators will closely communicate with subjects to improve compliance of subjects. This will help to reduce the informational bias.

